8.2 Calculation Formulas for the Parametric Win Ratio

The WHO primary endpoint is a categorical variable with 9 categories labeled 0 to 8 where 0 represents no clinical or virological evidence of infection and category 8 represents death. Because there are 9 possible values, the probability distribution of the primary endpoint within each treatment group can be described by a set of 9 probabilities which sum to 1. We will use notation π_{gj} to denote the probability that the primary endpoint of a patient in group g takes the value j (see Table 3). Using this notation, the probability that a patient in group g has a better outcome (win) than a patient in group h can be calculated by the expression:

$$W_{g:h} = W_{g:h}(\boldsymbol{\pi}) = \Pr(Y^g < Y^h) = \sum_{j=0}^7 \Pr(Y^g = j) \Pr(Y^h > j) = \sum_{j=0}^7 \pi_{gj} (\pi_{h,j+1} + \dots + \pi_{h,8})$$

and this expression holds for all $g, h = 1, 2, \dots, 6$. We use the notation $W_{g:h} = W_{g:h}(\boldsymbol{\pi})$ to emphasize that $W_{g:h}$ is implicitly a function of the unknown π_{gj} 's as defined in Table 3. The win ratio comparing groups g versus h is then given by

$$\text{Win-Ratio}_{g:h} = \frac{W_{g:h}}{W_{h:g}}$$

Hypothesis #1 (HCQ). The win ratio for Hypothesis #1 is a stratified version of the win ratio. It first randomly selects a patient from one of the HCQ groups (groups 2, 4, or 6) and then randomly selects a comparison patient from the corresponding non-HCQ group within the same AZM stratum, such that group 2 is paired with group 1, group 4 is paired with 3, and group 6 is paired with 5. The win ratio is the probability that the patient receiving HCQ has a better outcome than the patient not receiving HCQ divided by the probability that the patient receiving HCQ has a worse outcome than the patient not receiving HCQ. Mathematically, this turns out to be equivalent to a weighted average of 3 pairwise win ratios for groups 2 versus 1, 4 versus 3, and 6 versus 5. Specifically, the calculation formula for the hypothesis #1 win ratio is

$$\text{Win-Ratio}^{\text{HCQ}} = \left(\frac{n_1 + n_2}{n} \right) \frac{W_{2:1}}{W_{1:2}} + \left(\frac{n_3 + n_4}{n} \right) \frac{W_{4:3}}{W_{3:4}} + \left(\frac{n_5 + n_6}{n} \right) \frac{W_{6:5}}{W_{5:6}}$$

where n_g is the number of participants in the g -th treatment stratum and $n = n_1 + \dots + n_6$ is the total sample size.

Hypothesis #2 (AZM). The win ratio for Hypothesis #2 is a stratified version of the win ratio. It first randomly selects a patient from one of the randomized AZM groups (groups 3 or 4) and then randomly selects a comparison patient from the corresponding non-AZM group within the same level of HCQ, such that group 3 is paired with 1 and group 4 is paired with 2. The win ratio is the probability that the patient receiving AZM has a better outcome than the patient not receiving AZM divided by the probability that the patient receiving AZM has a worse outcome than the patient not receiving AZM. Mathematically, this turns out to be equivalent to a weighted average of 2 pairwise win ratios for groups 3 versus 1 and 4 versus 2. Specifically, the calculation formula for the hypothesis #1 win ratio is

$$\text{Win-Ratio}^{\text{AZM}} = \left(\frac{n_1 + n_2}{n_1 + n_2 + n_3 + n_4} \right) \frac{W_{2:1}}{W_{1:2}} + \left(\frac{n_3 + n_4}{n_1 + n_2 + n_3 + n_4} \right) \frac{W_{4:3}}{W_{3:4}}$$

Table 3. Notation for defining the distribution of WHO categories within each treatment group

	Group 1	Group 2	Group 3	Group 4	Group 5	Group 6
0	π_{10}	π_{20}	π_{30}	π_{40}	π_{50}	π_{60}
1	π_{11}	π_{21}	π_{31}	π_{41}	π_{51}	π_{61}

2	π_{12}	π_{22}	π_{32}	π_{42}	π_{52}	π_{62}
3	π_{13}	π_{23}	π_{33}	π_{43}	π_{53}	π_{63}
4	π_{14}	π_{24}	π_{34}	π_{44}	π_{54}	π_{64}
5	π_{15}	π_{25}	π_{35}	π_{45}	π_{55}	π_{65}
6	π_{16}	π_{26}	π_{36}	π_{46}	π_{56}	π_{66}
7	π_{17}	π_{27}	π_{37}	π_{47}	π_{57}	π_{67}
8	π_{18}	π_{28}	π_{38}	π_{48}	π_{58}	π_{68}

Note: $\pi_{g1} + \pi_{g2} + \dots + \pi_{g8} = 1$ for all $g = 1, 2, \dots, 6$.

A point estimate of the win ratio can be calculated using the "plug-in" method by substituting (i.e. plugging in) data-based estimates $\hat{\pi}_{gj}$ in place of the unknown π_{gj} 's in the calculation formulas given above. This leads to estimates of the form

$$\begin{aligned} \widehat{\text{Win-Ratio}}^{\text{HQC}} &= \left(\frac{n_1 + n_2}{n}\right) \frac{\widehat{W}_{2:1}}{\widehat{W}_{1:2}} + \left(\frac{n_3 + n_4}{n}\right) \frac{\widehat{W}_{4:3}}{\widehat{W}_{3:4}} + \left(\frac{n_5 + n_6}{n}\right) \frac{\widehat{W}_{6:5}}{\widehat{W}_{5:6}} \\ \widehat{\text{Win-Ratio}}^{\text{AZM}} &= \left(\frac{n_1 + n_2}{n_1 + n_2 + n_3 + n_4}\right) \frac{\widehat{W}_{2:1}}{\widehat{W}_{1:2}} + \left(\frac{n_3 + n_4}{n_1 + n_2 + n_3 + n_4}\right) \frac{\widehat{W}_{4:3}}{\widehat{W}_{3:4}} \\ \text{where } \widehat{W}_{g:h} &= \sum_{j=0}^7 \hat{\pi}_{gj} (\hat{\pi}_{h,j+1} + \dots + \hat{\pi}_{h,8}), \quad g, h = 1, 2, 3, 4, 5, 6, \end{aligned}$$

and $\hat{\pi}_{gj}$ is a data-based estimator of π_{gj} . For example, in a simple (non-Bayesian) nonparametric analysis we could plug in $\hat{\pi}_{gj} = n_{gj}/n_g$, where n_{gj} is the number of participants in group g with a WHO score equal to j . The primary analysis method is similar to this but uses Markov Chain Monte Carlo methods for inference and will estimate π_{gj} 's parametrically using a statistical model as defined in Section 8.3.

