8 ANALYSIS OF THE PRIMARY ENDPOINT

8.1 Parametric Win Ratio Analysis

The primary endpoint analysis will focus on assessing the overall effects of standard of care plus HCQ versus no HCQ (Hypothesis #1) and AZM versus no AZM (Hypothesis #2), as detailed in Section 3.1. Analysis will be performed in the intention-to-treat (ITT) population, as defined in Section 3.1. The analytic approach will be a model-based parametric implementation of the win ratio framework. [1] In a conventional win ratio analysis, the win ratio statistic is calculated by forming all possible pairs of 1 participant from the treatment group and 1 participant from the control group and then dividing the proportion of pairs for which the treated patient has a better outcome by the proportion of pairs for which the untreated patient has a better outcome. The PROTECT trial analysis will estimate this same underlying win ratio quantity but will do so parametrically using a statistical model. The parametric approach was chosen because it facilitates analysis in a Bayesian statistical framework using a range of Bayesian prior distributions. A Bayesian nonparametric implementation of the win ratio with a non-informative prior distribution was tested in simulations prior to trial launch and was found to be anti-conservative in the sense that the prior distribution assigned high prior probability to the hypothesis of large or small win ratio and this led to high probability of a spurious signal during interim analyses. The underlying quantities to be estimated in this analysis are as follows:

Win Ratio for Hypothesis #1 (HCQ versus no HCQ): The win ratio for HCQ versus no HCQ is defined as the probability that a randomly selected patient who was randomized to HCQ has a better outcome than a randomly selected patient from the same AZM subgroup who was randomized to no HCQ divided by the probability that a randomly selected patient who was randomized to HCQ has a worse outcome than a randomly selected patient from the same AZM subgroup who was randomized to no HCQ.

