The main effects SD = 0.3537 was chosen to imply that odds ratios for HCQ versus no HCQ and AZM versus no AZM are between 0.5 and 2.0 with 95% probability assuming that the interaction effects are zero. The interaction SD = 0.2651 was chosen to imply that the ratio of odds ratios for HCQ versus no HCQ across two levels of AZM and the ratio of odds ratios for AZM versus no AZM across two levels of HCQ would each be between 0.8 and 1.25 with 80% probability. The intercept parameters θ_k will be assigned central t distributions with 3 degrees of freedom and SD = 10 subject to the constraint $\theta_0 < \theta_2 < \dots < \theta_7$, which is the default prior in the R package 'brms'. To explore sensitivity to the choice of prior, the analysis will be repeated using two alternative forms for the prior distribution. The first alternative prior distribution will be the same as above but will set $\delta_1 = \delta_2 = 0$ with 100% probability. The second alternative prior will assign a non-informative improper uniform distribution to the set of main effects and interaction terms. Additional prior distributions may be implemented post-hoc for manuscript presentations or by request of external reviewers and stakeholders.

Computation

Posterior means and credible intervals for the Win Ratio quantities of interest will be calculated using Hamiltonian Markov Chain Monte Carlo (MCMC) simulations as implemented in the R package 'brms'. [4,4] To reduce Monte Carlo error, we will generate a large number of simulated parameter values and will perform graphical and other diagnostic checks to ensure convergence. To perform inference on Win-Ratio^{HCQ} and Win-Ratio^{AZM} we note that each of these quantities is a function of the cell probabilities $\boldsymbol{\pi}$ defined in Table 3 which in turn are functions of the model parameters $\Theta = (\theta_0, \theta_1, \theta_2, \theta_3, \theta_4, \theta_7, \theta_6, \theta_7, \mu, \gamma_1, \gamma_2, \delta_1, \delta_2)$. We use notation Win-Ratio^{HCQ}(Θ) and Win-Ratio^{AZM}(Θ) to denote the value of the win ratios as a function of unknown model parameters. Posterior mean point estimates of the win ratios will be calculated as

$$\begin{aligned}\widehat{\text{Win-Ratio}}^{\text{HCQ}} &= \frac{1}{M} \sum_{i=1}^M \text{Win-Ratio}^{\text{HCQ}}(\Theta^{(i)}) \\ \widehat{\text{Win-Ratio}}^{\text{AZM}} &= \frac{1}{M} \sum_{i=1}^M \text{Win-Ratio}^{\text{AZM}}(\Theta^{(i)})\end{aligned}$$

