8.6 Contingency for Violation of Proportional Odds Assumption

The proportionality assumption underlying the proportional odds model will be assessed by examining plots of empirical cumulative logits across treatment groups and comparing observed versus model-predicted probabilities. If there is substantial evidence of an unacceptable degree of model misspecification (e.g. the empirical cumulative logits from different treatment groups are clearly crossing) then a nonparametric instead of parametric win ratio analysis will be presented. To implement a Bayesian nonparametric version of the win ratio analysis, cell probabilities underlying the win ratio calculation (Table 3) will be estimated empirically by assigning noninformative independent Dirichlet distributions to the set of category probabilities within each treatment group. Other details of the calculations are essentially identical to those described for the primary analysis. The prior for this nonparametric Bayesian analysis was chosen for simplicity and computational convenience and may be revised in a subsequent version of the Statistical Analysis Plan.

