11 INTERIM ANALYSES

The primary objective of interim analyses is to ensure the safety of the participants enrolled in the trial and to evaluate the accumulating safety and efficacy data by treatment group to test for possible differences favoring any of the randomized treatments or treatment combinations. In addition, interim monitoring will involve a review of participant recruitment, compliance with the study protocol, status of data collection, an assessment of whether control group event rates are consistent with the rates hypothesized in the sample size calculations, and other factors which reflect the overall progress and integrity of the study including potential geographic differences.

An independent DSMB will review safety data on a regular basis according to the schedule specified in the DSMC charter. A team of one or two independent statisticians (i.e., the DSMB reporting statisticians) will be the only individuals (aside from the DSMB) with knowledge of interim outcomes by treatment group. Safety listings and tabular summaries will be generated regularly for the DSMB review. Unplanned meetings may be called if the DSMB members deem it to be necessary. The frequency of generating/sending these tables and listings to the DSMB is specified in the DSMC Charter.

Interim efficacy analyses will focus on the primary endpoint (World Health Organization ordinal scale) and death during the index hospitalization. Analyses will be performed both for the comparison of hydroxychloroquine versus no hydroxychloroquine (Hypothesis #1) and for the comparison of azithromycin versus no azithromycin (Hypothesis #2). The first pre-planned interim review of efficacy data will be performed after completion of data collection for the primary endpoint of the first 75 participants and subsequent pre-planned efficacy reviews will be performed approximately bi-weekly or based on a schedule specified in the DSMB charter. Considerations for multiple testing of the accumulating trial data are discussed in Section 11.1.

Statistical methods for interim analyses will be identical to those described in Section 8 for the final analysis. For the WHO scale primary endpoint, the statistical framework will be a Bayesian parametric win ratio analysis based on the proportional odds model. For mortality, the statistical framework will be a Bayesian logistic regression analysis. Guidelines proposed to the DSMB for interpretation of interim results are summarized in Table 5:

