Table 5. Proposed guidelines for DSMB statistical monitoring

	Definition	Monitoring Guideline
Moderate efficacy.	Win Ratio ≥ 1.25 favoring study drug over no study drug	Signal if probability is $>80\%$
Any efficacy	Win Ratio >1.0 favoring study drug over no study drug	Signal if probability is $>95\%$

Inefficacy	Win Ratio <1.0 favoring no study drug over study drug	Signal if probability is >80%
Moderate harm	Win Ratio <0.9 favoring no study drug over study drug	Signal if probability is >75%

Note: Study drug refers to the comparison of HCQ versus no HCQ (hypothesis #1) or the comparison of AZM versus no AZM (hypothesis #2). Win ratios will be estimated for both the primary endpoint and death during the index hospitalization.

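### The stratified win ratio defined in SAP 8.1 is not, in general, equal to the weighted average of pairwise win ratios printed in 8.2

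*SAP*

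**What the plan says.** Section 8.1 defines the HCQ win ratio as the probability that an HCQ patient "has a better outcome than a randomly selected patient from the same AZM subgroup who was randomized to no HCQ divided by the probability" of a worse outcome under the same pairing. Section 8.2 restates this as a sampling scheme: draw an HCQ patient from group 2, 4 or 6, draw a comparator from the matching group 1, 3 or 5, then divide the probability of winning by the probability of losing. It continues: "Mathematically, this turns out to be equivalent to a weighted average of 3 pairwise win ratios". The formula printed after that puts weights (n1+n2)/n, (n3+n4)/n and (n5+n6)/n on W2:1/W1:2, W4:3/W3:4 and W6:5/W5:6.

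The same claim is made for AZM: "equivalent to a weighted average of 2 pairwise win ratios for groups 3 versus 1 and 4 versus 2". The plug-in estimators that close Section 8.2 repeat the averaged form, and the text adds: "The primary analysis method is similar to this but uses Markov Chain Monte Carlo methods for inference".

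Three other places carry the formula further:
- Section 8.4, sensitivity prior: "The second alternative prior will assign a non-informative improper uniform distribution to the set of main effects and interaction terms".
- Section 8.6, nonparametric contingency: "Other details of the calculations are essentially identical to those described for the primary analysis".
- Section 11, interim analyses: "Statistical methods for interim analyses will be identical to those described in Section 8 for the final analysis".

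**The concern.** A ratio of two weighted sums is not the weighted mean of the separate ratios with the same weights. The SAP asserts the identity without limiting it to equal effects across strata. Its primary model (Section 8.3) includes interaction terms δ1 and δ2, whose purpose is to let the HCQ effect differ between AZM groups.

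As written, the quantity computed is therefore not the estimand defined. It enters the win-ratio posterior means, their credible intervals, and the Table 5 probabilities, which are judged against fixed cut-offs of 1.0, 1.25 and 0.9. If the discrepancy runs mostly in one direction, it adds efficacy signals and suppresses inefficacy signals.

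**Working it through.** **Notation.** For stratum s, W_s is the probability that the treated patient wins, L_s the probability that the treated patient loses, w_s the stratum weight, and R_s = W_s/L_s.

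**Defined quantity (8.1, and the 8.2 sampling scheme).** By total probability, R_def = Σ w_s W_s / Σ w_s L_s.

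**Printed quantity (8.2).** R_print = Σ w_s (W_s/L_s).

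**Gap.** Since Σ w R L = Σ w W, Cov_w(R, L) = E_w[W] − E_w[R]·E_w[L]. Dividing by E_w[L] gives

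R_print − R_def = −Cov_w(R, L) / E_w[L].

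This is zero only if the weighted covariance is zero, for example with equal win ratios or equal loss probabilities. A stratum with a higher win ratio usually has a lower loss probability, so the covariance is usually negative and the printed form is usually higher.

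**Hand examples (equal weights).**
- W = (0.6, 0.2), L = (0.2, 0.6): defined 0.4/0.4 = 1.000; printed (3 + 0.333)/2 = 1.667.
- W = (0.2, 0.3), L = (0.2, 0.25): defined 0.25/0.225 = 1.111; printed (1.0 + 1.2)/2 = 1.100. The printed form can be lower.
- W = (0.5, 0.3, 0.4), L = (0.3, 0.5, 0.4): defined 1.000; printed (1.667 + 0.6 + 1)/3 = 1.089. Swapping the arms again gives 1.089, so each arm appears better than the other. With weights 40/40/20% the figure is 1.107 in both directions.

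**The SAP's proportional odds model.** Assumptions not in the SAP: stratum shares 40/40/20%, and group 1 WHO 0–8 probabilities 2/25/23/12/12/6/6/4/10%. With HCQ odds ratios 2, 0.5 and 1 in the three strata:
- W = 0.516, 0.320, 0.418; L = 0.299, 0.542, 0.418; R = 1.725, 0.590, 1.000.
- Defined: (0.2064 + 0.1280 + 0.0836)/(0.1196 + 0.2168 + 0.0836) = 0.418/0.420 = 0.995.
- Printed: 0.690 + 0.236 + 0.200 = 1.126.

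With μ = 0 and interactions at +1 and −1 prior SD (0.2651), defined is 1.041 and printed 1.055. With interactions zero, odds ratio 1.5, γ1 = 0.35 and γ2 = −0.7, they are 1.3728 and 1.3731.

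**Draws from the Section 8.4 primary prior** (200,000 per baseline; SDs 0.3537 and 0.2651; shares 40/40/20%). Three assumed WHO 0–8 distributions: A = even; B = 5/30/25/8/10/5/5/4/8%; C = 2/10/18/12/18/10/10/8/12%.
- Printed higher in 97.6–99.8% of draws; median excess 0.5–0.6%, mean 0.8–1.0%.
- P(win ratio > 1): 0.510–0.513 printed, 0.500 defined.
- Printed form above 1 under both arm labellings: 2.1–2.3% of draws. Under the definition this cannot happen.

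**Null trials.** The model-based rows use a Laplace approximation with 1,500 posterior draws; the fallback uses exact Dirichlet posteriors. Table 5 rules were applied to both forms on the same draws, with 2,000 trials per setting except where noted. Entries are the percentage of trials signalling, printed / defined; a dash means not tabulated.

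| Analysis | N | Baseline | Efficacy | Inefficacy |
|---|---|---|---|---|
| Primary prior (separate check, 500 trials) | 75 | B | 1.0 / 0.8–1.0 | 11.0–11.2 / 12.6–12.8 |
| Primary prior | 500 | B | 4.1 / 3.7 | 16.5 / 18.1 |
| Primary prior | 500 | C | 5.0 / 4.5 | 15.6 / 17.0 |
| Flat prior | 75 | B | 18.5 / 6.8 | 6.9 / 20.2 |
| Flat prior | 75 | C | 18.6 / 6.5 | 7.6 / 20.8 |
| Flat prior | 500 | B | 7.3 / 4.6 | – |
| Flat prior | 500 | C | 8.3 / 5.8 | – |
| Fallback, Dirichlet(1) assumed | 75 | B, C | 2.9–4.0 / 0.8–1.5 | 6.2–6.6 / 14.0–14.4 |
| Fallback, Dirichlet(1) assumed | 500 | B, C | – | 12.7–13.0 / 18.5–19.0 |

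Under the primary prior at N = 500, 8 (B) and 9 (C) of 2,000 trials signalled efficacy only under the printed form, and none only under the defined form. The posterior mean was 1.020 printed and 1.013 defined. With interactions fixed at zero (the first alternative prior), no signal rate differed.

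**The case against.** The strongest reply is that the error hardly touches the primary analysis. The posterior mean moves from 1.013 to 1.020, and at the first planned efficacy look (75 participants) the primary-prior efficacy rates are practically the same. Table 5 is headed as proposed guidelines, and Section 11.1 sets no threshold for definitive evidence. The large differences arise in a sensitivity prior and in a contingency whose Dirichlet parameter is not given and whose prior the SAP says may be revised. All of this is correct, and it limits the weight of the point.

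Four further limits also stand:
- Not every result is affected. The pairwise odds ratios (8.7) and the continuation-ratio endpoints (Section 9) do not use this formula.
- The Table 5 note says "Win ratios will be estimated for both the primary endpoint and death during the index hospitalization", but the SAP does not say that the death win ratio is combined across strata by the same formula. No weight is placed on that endpoint here.
- The sampling scheme implies weights n2/(n2+n4+n6) and so on, not (n1+n2)/n. These agree only when the HCQ-to-control ratio is the same in every stratum, which 1:1 randomisation gives approximately.
- Consistency could instead be restored by keeping the average and redefining the estimand.

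None of this rescues the equivalence statement. No section restricts it to homogeneous effects, and the averaged form recurs in the estimators, so it is not an isolated misprint.

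**Conclusion.** The concern holds. The claimed equivalence is false in general, and this follows from algebra alone, without assumed data. The win ratio that the SAP computes is not the one it defines, and the difference nearly always favours the study drug.

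The size is modest in the primary analysis: about 1% on the win ratio, and about half a percentage point or less on null efficacy signals at 500 participants. It is essentially nil with interactions fixed at zero. It is material under the flat sensitivity prior and in the nonparametric fallback, especially at 75 participants.

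These sizes are for HCQ only and rest on assumed stratum shares, WHO distributions and, for the fallback, a Dirichlet parameter that the SAP does not give. The point should be fixed because it concerns the primary estimand and costs little; it would hardly change a primary conclusion by itself.

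**What to change.** In Section 8.2, replace the HCQ formula and its plug-in version by

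Win-Ratio^HCQ = (w1·W2:1 + w2·W4:3 + w3·W6:5) / (w1·W1:2 + w2·W3:4 + w3·W5:6),

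with the existing weights w1 = (n1+n2)/n, w2 = (n3+n4)/n, w3 = (n5+n6)/n. State these weights in the definition, or use n2, n4 and n6 over their sum if the sampling scheme is to hold exactly.

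For AZM use

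Win-Ratio^AZM = (v1·W3:1 + v2·W4:2) / (v1·W1:3 + v2·W2:4),

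with v1 = (n1+n3)/(n1+n2+n3+n4) and v2 = (n2+n4)/(n1+n2+n3+n4). This also removes a separate error: the printed AZM formula uses the HCQ pairs (2 versus 1, 4 versus 3), although its text names 3 versus 1 and 4 versus 2.

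Delete both equivalence sentences. Keep the prespecified posterior mean and equal-tailed interval. Keeping the average and redefining the estimand would also be consistent, but would leave a measure that is not reciprocal when the arms are swapped.

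The cost is a wording change in Section 8.2 and one line of code per formula. The 14% false-signal simulation in Section 11.1 needs rerunning only if it used the printed formula. Section 8.3 says the sample size calculations omitted interactions; if that simulation did too, little should change.
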